## Randomization

Using STATA software, the Statistician will generate a random allocation sequence stratified by GA at birth (GA <28 weeks and >28 weeks) to balance representation of the youngest and sickest infants. We will use permuted block randomization for each stratum, with block sizes of 2, 4, and 6 and a 1:1 treatment allocation. The Statistician will upload the sequence into REDCap, have no contact with subjects, and will be independent of all assessment procedures. REDCap's secure randomization feature prevents the study team from viewing the treatment allocation sequence, ensuring allocation concealment. Research assistants will enroll and collect baseline data before randomization. The Principal Investigator (PI) / Clinical Research Coordinator (CRC) will randomize each family after baseline survey completion to minimize dropout effects on randomization.

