## Eligibility Criteria

### Inclusion Criteria:

- English-speaking parents
- Parents preterm infants born 25 0/7-31 6/7 weeks gestational age (GA)
- Parents who had a singleton or twin birth
- Parents 18 years of age or older

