## Outcome Measures

Measure Title	Maternal Self-Rating of Depression
Measure Description	Patient-Reported Outcomes Measurement Information System (PROMIS) 8a Higher scores indicate higher levels of depression: T-score: standardized score mean of 50 and standard deviation (SD) of 10
Time Frame	Assessed at Baseline 14 days post-baseline (T2), 28 days post-baseline (T3), and 30 days after infant discharge from the NICU (T4). Change from Baseline to 30 days after infant discharge from the NICU (T4) Reported.
Measure Title	Maternal Self-Rating of Anxiety
Measure Description	Patient-Reported Outcomes Measurement Information System (PROMIS) 8a Higher scores indicate higher levels of anxiety: T-score: standardized score mean of 50 and standard deviation (SD) of 10
Time Frame	Assessed at Baseline, 14 days post-baseline (T2), 28 days post-baseline (T3), and 30 days after infant discharge from the NICU (T4). Change from Baseline to 30 days after infant discharge from the NICU (T4) Reported.
Measure Title	Receipt of Mother's Human Milk
Measure Description	(exclusive, partial, none).
Time Frame	Assessed at Baseline, 14 days post-baseline (T2), 28 days post-baseline (T3). Reported here is 28 days post-baseline (T3).
Measure Title	Z Score of Weight Gain at 36 Weeks Corrected Gestational Age
Measure Description	Z-score method; Z score $\Delta$ weight (g), Birthweight (g) - infant weight (g) at 36 weeks corrected gestational age
Time Frame	Calculated for the date that infant is 36 weeks corrected gestational age
Measure Title	NICU Length of Stay
Measure Description	Days of NICU hospitalization (calculated from days between date of birth to date of discharge from NICU)
Time Frame	Date of NICU discharge will be assessed until study completion, with maximum of 1 year
Measure Title	Infant Hospital Readmissions and Emergency Department Visits Within 30 Days of Infant Discharge.
Measure Description	Coded as Yes/No and extracted from the infant's electronic health record. Mothers were also asked "Did your infant have any re-hospitalizations or emergency department visits within 30 days of discharge?", to ensure all rehospitalizations and ED visits were captured.
Time Frame	Readmissions/ER visits counted within 30 days of discharge will be assessed date of NICU discharge will be assessed until study completion, with maximum of 1 year

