### Power

We aimed to enroll at least 60 mothers (30 mothers per arm), with planned over recruitment to account for up to 20% loss to follow-up (i.e., 72 infants) during the pilot trial. Because we did not have reliable estimates for the confidence intervals, standard errors, or mean differences for our outcomes a priori, our sample size was based on Whitehead's recommendations to have at least 20 persons per treatment arm in a pilot trial when expecting a small standardized difference ( $\delta=0.2$ ) to achieve at least 80% in the main trial. Because our emphasis was on feasibility, this pilot trial was not powered to detect statistically significant changes in outcome and mediating variables between arms.

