### Analysis

REDCAP data will be exported to Stata 15 software, where we will analyze sources of missing data and calculate descriptive/summary statistics. We will graph trends for all variables over infant Day of Life (DOL) and CGA, comparing boxplots between arms and over time. We will compute means and 95% CIs for changes from baseline (T1 to T2-4) for each outcome by arm. At each follow-up (T2-4), we will compute mean differences and 95% CI between arms to evaluate trends in outcomes. Mothers with multiple births will have one infant randomly selected for analysis. We will not test for statistically significant differences between groups in outcome measures or estimate effect sizes in this pilot study, because the primary purpose is to determine feasibility of our procedures to inform the planning and design of a larger trial.

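### Analysing one randomly drawn twin is valid but inefficient; averaging a mother's two twins targets the same mean with an expected 95% CI about 1–6% narrower under assumed inputs.

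*Combined protocol and SAP*

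**What the plan says.** The Inclusion Criteria admit "Parents who had a singleton or twin birth". Under Randomization, the study team "will randomize each family after baseline survey completion", so both twins always share an arm. The allocation is stratified by gestational age at birth, not by singleton or twin birth.

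The Analysis section then says "Mothers with multiple births will have one infant randomly selected for analysis". It gives no reason for the draw, no method or seed, and no analysis that uses the second twin. It also does not say what happens when the drawn twin has no value but the co-twin does.

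The results to be reported are descriptive: "We will compute means and 95% CIs for changes from baseline (T1 to T2-4) for each outcome by arm", and at each follow-up "we will compute mean differences and 95% CI between arms to evaluate trends in outcomes". The same section rules out between-arm tests because the aim is feasibility, to inform a larger trial.

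**The concern.** Four of the six measures under Outcome Measures concern the infant: mother's milk, weight z-score, NICU length of stay, and readmissions or emergency visits. For these, a twin mother could supply two observations but supplies one, chosen by chance. The choice adds variation that comes from neither the treatment nor the families, and a different draw from the same families would give different estimates.

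What is at stake is precision. The Power section says that reliable standard errors and mean differences were not available in advance, so the pilot's estimates and intervals are part of what it hands to the larger trial. Drawing one infant also means that the within-pair correlation cannot be estimated, although a larger trial that admits twins would need it.

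**Working it through.** **Inputs.** From the documents: 1:1 allocation by family, 30 mothers per arm (60 in total), singleton or twin births, results as means and mean differences with 95% CIs. Not in the documents and therefore assumed: p, the share of mothers with twins, 15–35%; ρ, the within-pair correlation, 0.3–0.7, with 0.9 as a high case. Singletons and twins are given the same infant-level variance σ².

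**The plan's own figures.** The plan states no precision for infant outcomes. The only derived figure in the Power section is the recruitment target of 72, which is 60 × 1.2. Nothing below depends on it.

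**Same target.** A fair draw from a pair has expectation equal to the pair mean, and each mother keeps a weight of one. Both methods therefore estimate the mother-weighted arm mean and its difference between arms.

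**Variance.** For a twin mother, the variance of a random pick is σ² and that of the pair mean is σ²(1 + ρ)/2. Over all mothers, the ratio of the two variances is

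(1 − p) + p(1 + ρ)/2 = 1 − p(1 − ρ)/2.

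CI width scales with its square root. The equivalent number of mothers is 60 divided by the ratio.

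| p | ρ | Variance ratio | CI narrower by | Equivalent to 60 mothers with the draw |
|---|---|---|---|---|
| 0.15 | 0.7 | 0.9775 | 1.1% | 61.4 |
| 0.25 | 0.5 | 0.9375 | 3.2% | 64.0 |
| 0.35 | 0.3 | 0.8775 | 6.3% | 68.4 |
| 0.15 | 0.9 | 0.9925 | 0.4% | 60.5 |
| 0.35 | 0.9 | 0.9825 | 0.9% | 61.1 |

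At ρ = 1 there is no gain.

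**Check by simulation** (20,000 trials per setting, 30 mothers per arm, t-based 95% CI):

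- p = 0.2, ρ = 0.5: mean CI width 1.028 SD with the draw and 1.002 SD with the twin mean, ratio 0.975. The formula gives √0.95 = 0.975. Coverage was 0.950 for both.
- p = 0.3, ρ = 0.3: ratio 0.946. p = 0.2, ρ = 0.8: ratio 0.990.
- A Yes/No outcome at 20% (p = 0.2, latent ρ = 0.5): ratio 0.964.
- Twins shifted by 0.5 SD from singletons (p = 0.2, ρ = 0.5): the arm mean was 0.101 under both methods, which supports the shared target.

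The narrowing is an average. In single simulated trials the twin-mean interval was the narrower one in about 70–92% of cases, depending on the setting.

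**The case against.** The strongest reply is that this is a choice between two valid mother-level estimators, in a pilot that is not powered on these outcomes and will not test them. No decision in the documents turns on an interval about 3% narrower. That stands, and it limits the point to a cheap improvement. It does not reverse the direction.

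Some further objections also stand:

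- **SD for the larger trial.** The SD of a mix of singleton values and pair means is not an infant-level SD. In the central case its variance is 6.25% too low, so a larger trial analysing one infant per family and sized from it would be about that much too small. The one-infant rule gives the infant-level SD directly. Any replacement must report that SD as well.
- **Scope.** Mother's milk has three categories and no mean as coded. Twins of one mother may also be fed alike, so it gains only where they differ. Boxplots and medians do not share the equivalence shown for means.
- **Missing twins.** If one twin's value is missing for reasons related to outcome, using the other twin's value may not target the same quantity as an infant drawn in advance.
- **Data.** The documents do not say that co-twin data are collected. The supplementary maternal question on readmissions and emergency visits refers to a single infant, and the Power section describes the recruitment target as 72 infants although it counts mothers.

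A reader might also set the noise of the draw, √(p(1 − ρ)/30) = 0.065 SD of the between-arm difference at p = 0.25 and ρ = 0.5, against the standardised difference of 0.2 in the Power section. The documents do not support that comparison. The 0.2 is an input to a rule for sizing a pilot, not an expected difference in these infant outcomes. The noise also adds in squares: the SD of the difference is √(2/30) = 0.258 with the draw and √(2 × 0.9375/30) = 0.250 with twin means.

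**Conclusion.** The point holds as a modest loss of efficiency. A reader might infer that the random draw biases the comparison or invalidates the intervals. It does neither: whole families are randomised, one infant per mother is kept, and simulated coverage was nominal.

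The size rests on the assumed twin share and correlation and on equal infant-level variance in singletons and twins. It is clearest for length of stay, weight z-score and readmissions or emergency visits. The direction, for means and proportions with complete pairs, needs only ρ below 1.

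**What to change.** Replace the sentence on multiple births in the Analysis section with wording such as:

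> For means and proportions of infant outcomes, each mother contributes one value: the infant's value for singletons, and the mean of the two infants' values for twins (for Yes/No or category outcomes, the share of the pair in that category). If only one twin has a value, that value is used. Between-arm differences use Welch or robust standard errors. The infant-level SD and the within-pair correlation are also reported for planning the larger trial.

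The standard errors are specified because pair means vary less than singleton values and birth type is not a stratification factor. Boxplots and medians should stay at infant level or use the one-infant draw. The draw is otherwise kept as a sensitivity analysis, with its method and seed recorded.

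The cost is abstraction of the co-twin's discharge date, 36-week weight, feeding status and readmission or emergency record, and asking the maternal readmission and emergency question for each twin. No extra participants or visits are needed. The report should state that the mother-level SD must not be used as an infant-level SD when the main trial is sized.
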